	
additional 3 patients will be enrolled at this dosage level. Assessment of DLT for dose escalation will be made after the 3 additional patients have had a study visit at least 3 weeks after receiving their first dose of vaccine. If none of these latter 3 patients have DLT (i.e., 1 DLT in the 6 total patients), then patients may begin enrolling into cohort 2. If 2 patients have DLT at the lowest dosage level, dosing will be de-escalated to 1×10^8 particles.
 
2) Cohort 2: Three patients will receive Ad5 [E1-, E2b-]-CEA(6D) at a dose of 1×10^{10} particles SQ in 0.5 mL every 3 weeks for 3 immunizations. Assessment of DLT for dose escalation will be made after all patients in this cohort have had a study visit at least 3 weeks after receiving their first dose of vaccine. If there are no DLT, then patients may begin enrolling into cohort 3. If there is 1 DLT then an additional 3 patients will be enrolled at this dosage level. Assessment of DLT for dose escalation will be made after the 3 additional patients have had a study visit at least 3 weeks after receiving their first dose of vaccine. If none of these latter 3 patients have DLT, then patients may begin enrolling into cohort 3.
 
3) Cohort 3: Six patients will receive Ad5 [E1-, E2b-]-CEA(6D) at a dose of 1×10^{11} particles SQ in 0.5 mL every 3 weeks for 3 immunizations. Assessment of DLT for proceeding to phase II enrollment will be made after all patients in this cohort have had a study visit at least 3 weeks after receiving their first dose of vaccine. If there is 0 or 1 DLT, then patients may begin enrolling into the phase II portion of the study.
 
4) Phase II Cohort (Cohort 4): An additional 12 patients will receive Ad5 [E1-, E2B-]-CEA(6D) at the MTD every 3 weeks for 3 immunizations.
 
5) Cohort 5: Beginning after the third dose of ETBX-011 for the 12th patient in cohort 4, enrollment in an additional higher dose cohort will be permitted. Six patients will receive Ad5 [E1-, E2b-]-CEA(6D) at a dose of 5×10^{11} particles SQ in 2.5 mL every 3 weeks for 3 immunizations. Assessment of DLT will be made after all patients in this cohort have had all 3 injections and been observed for at least 30 days after the last injection. If there are 0-1 DLT, then this will be declared the maximum feasible dose. If there are 2 or more DLT, then 1×10^{11} particles will be declared the MTD.
 
6) Cohort 6: Up to ten (10) will receive Ad5 [E1-, E2b-]-CEA(6D) at a dose of 5×10^{11} particles SQ in 1.0 mL every 3 weeks for 3 immunizations. Patients will be permitted to receive booster doses of Ad5 [E1-, E2b-]-CEA(6D) every 3 months for a period of one year following the first 3 treatments. In the event that a qualified patient undergoes reimaging prior to the completion of their initial 3 study immunizations and is found to have disease progression, the patient should continue on the immunization protocol because this could be a “flare reaction” associated with the vaccine which may be an inflammatory response. Patients will be required to have MRI/CT scans performed prior to initiation of treatment, at 3 month intervals +/- 1

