6. TREATMENT PLAN

Patients will be enrolled into successive dosage level cohorts of 3 or 6 patients and monitored for dose-limiting toxicity (DLT).

DLT (Based on NCI CTCAE version 4.0) is defined as any Grade 2, 3 or 4 immediate hypersensitivity reactions, Grade 3 or 4 fever that may possibly be associated with the immunization, Grade ≥ 2 autoimmune events except for vitiligo or fever for less than 2 days and less than 101.5 °F, Grade ≥ 2 allergic reactions (grade 2 is defined as generalized urticaria as defined by CTCAE version 4.0), or Grade ≥ 3 non-hematologic toxicity.

During dose escalation through the first three patients of cohort 3, there will be a minimum of 1 week between enrolling successive patients. The first patient will be called to check on their condition prior to enrolling the second patient since patients can be enrolled after 1 week of initiation of cohort 3. If no DLT have been observed at this point, then further enrollment can occur in cohort 3 and phase II component (Cohort 4) without the 1-week waiting period. Between dosage levels, through Cohort 3, assessment of DLT for dose escalation will be made after all patients in a cohort have had a study visit at least 3 weeks after receiving their first dose of vaccine and all the available safety data and laboratory results have been reviewed. Patients in cohort 5 may begin injections once all patients in cohort 4 have had at least their first injections and all patients in cohort 3 have had a study visit at least 3 weeks after receiving their first dose of vaccine. If DLT occurs in $<33\%$ of patients in a given dosage level cohort, progression to the next dosage level will proceed. If DLT occurs in $\geq 33\%$ of patients in a given cohort, the next lower dosage level will be defined as the maximum tolerated dose (MTD). If DLT occurs in $<33\%$ of patients in the highest dosage level tested, that dosage level will be defined as the MTD. In phase II (Cohort 4) and Cohort 5, if at any time the rate of DLT in patients enrolled is $\geq 33\%$, the MTD will be re-defined as the next lower dosage level. Additional details of this dose escalation and de-escalation plan are provided below and in Figures 3A, 3B and Table 3.

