- 6) Cohort 6: Up to ten (10) patients will receive Ad5 [E1-, E2b-]-CEA(6D) at a dose of 5×10^{11} particles SQ in 1.0 mL every 3 weeks for 3 immunizations. Patients will be permitted to receive booster doses of Ad5 [E1-, E2b-]-CEA(6D) every 3 months for a period of two years following the first 3 treatments. In the event that a qualified patient undergoes reimaging prior to the completion of their initial 3 study immunizations and is found to have disease progression, the patient should continue on the immunization protocol because this could be a “flare reaction” associated with the vaccine which may be an inflammatory response. Patients will be required to have MRI/CT scans performed prior to initiation of treatment, at 3 month intervals +/- 1 month for 12 months or if the investigator believes signs or symptoms are suggestive of progression or relapse. All patients will be followed for overall survival for a period of 24 months from initiation of treatment.
- 7) Patients will have 90 mL peripheral blood drawn prior to each immunization and approximately 3 weeks after the third immunization (Week 9) to determine whether there is an effect on the immune response at specific time points during the study and/or after a specific number of immunizations.
- 8) Time to progression will be measured using CT scans performed at approximately 3 month intervals (based on clinical standard of care).
- 9) For all patients, if scheduling conflicts arise, the scheduled 3-week interval between immunizations may be modified so that the interval between immunizations is between 20 and 28 days (3 weeks -1 day to 3 weeks +7 days). If the second and/or third immunization is delayed, the subsequent immunizations should occur no earlier than 20 days after the previous immunization.
- 10) The following safety events will trigger a temporary suspension of study vaccinations:
 - a) If one or more patients develop a Grade 4 allergic reaction without a clear attributable cause, other than study vaccine
 - b) Death not attributed to disease.

Assessment of these halting rules is a review of cumulative events for all study participants, and should not be confused with reasons for delaying or terminating the immunization schedule of any individual patient.

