8. STATISTICAL CONSIDERATIONS

8.1. Safety

We will evaluate safety continuously in a cohort. We will make our overall assessment of whether to escalate to the next dose level at least 3 weeks after the last patient in the previous cohort has received their first injection. This decision will be made by the medical monitor and the Principal Investigator. A note will be generated following the assessment decision and filed in study binder. A dosage level will be considered safe if <33% patients treated at a dose level experience DLT (i.e., 0 of 3, ≤ 1 of 6, ≤ 3 of 12, or ≤ 5 of 18 patients). DLT is defined in Protocol Section 6. Safety will be evaluated in 3 or 6 patients at each dosage level in phase I. Safety will continue to be monitored among additional patients treated at the MTD in phase II. A patient will be considered evaluable for safety if treated with at least one immunization. DLTs will be observed through 9 weeks to accommodate safety evaluation of all 3 product doses.

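### The latest protocol version gives two start conditions for the five-fold higher cohort 5 (about 42 days apart as written) and two booster durations for cohort 6 (one year or two)

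*Combined protocol and SAP*

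**What the plan says.** All references are to the latest protocol version in the file, the one that contains cohort 6.

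**Cohort 5 (5×10^11 particles; cohorts 3 and 4 receive 1×10^11).**
- Protocol Summary, Study Design item 5: "Beginning after the third dose of ETBX-011 for the 12th patient in cohort 4, enrollment in an additional higher dose cohort will be permitted".
- Section 6, Treatment Plan: "Patients in cohort 5 may begin injections once all patients in cohort 4 have had at least their first injections", together with the condition that "all patients in cohort 3 have had a study visit at least 3 weeks after receiving their first dose of vaccine".
- Section 6 also confines its own three-week assessment rule to the lower cohorts: "Between dosage levels, through Cohort 3, assessment of DLT for dose escalation will be made after all patients in a cohort have had" the three-week visit.
- Section 8.1 has a general rule with no such limit. Escalation is assessed "at least 3 weeks after the last patient in the previous cohort has received their first injection". It adds that "A dosage level will be considered safe if <33% patients treated at a dose level experience DLT".

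**Cohort 6 boosters.**
- Protocol Summary, Study Design item 6: permitted "every 3 months for a period of one year following the first 3 treatments".
- Section 6, item 6: a matching sentence, but with two years in place of one.
- Section 6.2.1 fixes the booster dose but gives no duration. Appendix 1 marks immunization only at Weeks 0, 3 and 6.

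**The concern.** These are instructions that staff act on, at the highest dose in the trial. Section 8.1 gives the escalation decision to the medical monitor and the Principal Investigator, who have two written gates for a five-fold step. The treating investigator has two written limits on repeat dosing. On both points Section 6, the treatment plan itself, is the more permissive text. An investigator who follows it exactly can depart from the Summary, either by escalating before the last cohort 4 patients have had all three doses or by giving more boosters than the Summary allows.

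The wording about enrollment in one place and injection in the other does not reconcile the cohort 5 texts. Enrollment comes before injection, so Section 6 can allow an injection before the Summary allows entry. Nor does Section 6's cohort 3 condition close the gap, because item 3 of the same section already requires those visits before cohort 4 opens.

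**Working it through.** No sample-size formula is involved; this is schedule arithmetic.

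**Inputs**
- Nominal dose interval: 21 days (Section 4.4 puts dose 2 at Day 21; Section 7.1.1 lists immunization visits at Weeks 0, 3 and 6).
- Allowed window: "the interval between immunizations is between 20 and 28 days" (Section 6, item 9).
- General floor before escalation: 3 weeks = 21 days after the last first injection (Section 8.1).
- Booster interval: 3 months; duration 12 or 24 months.

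**The plan's own window.** 21 − 1 = 20 days and 21 + 7 = 28 days, as stated.

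**Size of the step.** 5×10^11 / 1×10^11 = 5.

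**Gap between the two written gates.** Assume the twelfth patient is the last cohort 4 patient dosed. Section 6 opens at that patient's dose 1 and the Summary at dose 3, so the gap is two intervals:
- nominal: 2 × 21 = 42 days
- shortest: 2 × 20 = 40 days
- longest: 2 × 28 = 56 days

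**Gap if Section 8.1's floor is added to the Section 6 gate.** The earlier gate then moves to day 21:
- nominal: 42 − 21 = 21 days
- shortest: 40 − 21 = 19 days
- longest: 56 − 21 = 35 days

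**Exposure of the last cohort 4 patient when cohort 5 may start**

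| Reading | Doses received |
|---|---|
| Section 6 sentence alone | at least one |
| Section 6 plus the Section 8.1 floor | one or two (dose 2 falls between day 20 and day 28) |
| Summary | three |

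**Booster ceiling.** 12 / 3 = 4 under one year; 24 / 3 = 8 under two.

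**How each duration fits the rest of the plan.** Assume boosters are counted from the third dose, and scan and survival months from treatment start. The third dose falls at 42 / 30.44 = 1.38 months.
- Booster 4: 12 + 1.38 = month 13.4
- Booster 5: 15 + 1.38 = month 16.4
- Booster 8: 24 + 1.38 = month 25.4

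Cohort 6's required scans run for 12 months (±1 month per scan), and Section 7.2 and Appendix 1 request follow-up for 1 year. Survival follow-up runs to month 24. One year is therefore the closer fit to the scans and visits, though not an exact one. Under two years, boosters 5 to 8 fall after the last required scan, and booster 8 falls about 1.4 months after survival follow-up ends.

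**The case against.** The strongest reply is that no safety rule depends on which text is followed. The halting rules (Section 6, item 10), the stopping rules (Section 6.1) and the 33% DLT rule apply under either reading. Adverse event monitoring runs to 30 days after the last dose (Section 10.5). Boosters are optional, and a team that follows the stricter text on each point breaches nothing. All of this stands and limits the weight of the point. It does not remove the conflict, because no visible text tells the team to follow the stricter wording.

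A second reply is that Section 8.1 already prevents a start straight after the last first injection, so the real gap is nearer 21 days. That is a fair reading, but Section 6 restricts its own three-week rule to cohorts through 3 and then gives cohort 5 a specific sentence. Whether the general floor adds to that sentence is a matter of interpretation, so both figures are given.

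Three stronger readings are tempting and are not supported:
- **That later boosters would be given without monitoring or imaging.** Only cohort 6's mandatory scans end at 12 months. Section 6, item 8 and Appendix 1, note f provide standard-of-care scans with no such cap, and item 6 adds scans when symptoms suggest progression.
- **That one year is plainly the intended duration.** The scans and visits point toward one year, but the 24-month survival follow-up appears in both texts and sits closer to two. The documents do not settle it.
- **That the Summary's gate only needs copying into Section 6.** It depends on one patient's third dose. If that patient stops early (Sections 7.3.4 and 9), the condition can never be met as worded. Section 7.3.4 also allows up to 3 replacements per cohort, so the twelfth patient may not be the last one dosed.

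**Conclusion.** Both contradictions are real, and both lie inside one protocol version; they are not differences between a superseded text and its replacement. As written, the cohort 5 gates differ by about 42 days (40 to 56), falling to about 21 (19 to 35) if Section 8.1's floor is read into the Section 6 gate. Both figures assume that the twelfth patient is the last in cohort 4 to be dosed. The booster ceiling is about 4 or about 8 per patient still on treatment.

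The consequence is avoidable early escalation, uncertain cumulative exposure and protocol deviations, not unmonitored dosing. The Summary's gate is the better one to keep. Section 8.1 observes DLTs through 9 weeks so as to cover all three doses, and only the Summary's gate ensures that the last patient at the lower dose has reached the third. Even then, that patient is nominally at Week 6, so the 9-week observation is not complete. This should be fixed.

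**What to change.** **Cohort 5.** Replace the Section 6 sentence, and align the Summary, with one gate that can always be met: no cohort 5 enrollment or injection until every cohort 4 patient, including any replacement, has either received the third dose or discontinued. The existing rule of under 33% DLT applies unchanged, and no new DLT criterion is needed. A single gate is workable: the protocol version that precedes this one in the file uses one cohort 5 condition in both its Summary and its Section 6.

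**Cohort 6.** The sponsor confirms one booster duration and states it in both the Summary (item 6) and Section 6 (item 6). One year fits the required 12-month scans and the 1-year follow-up better. If two years is intended, correct the Summary and extend cohort 6's required scans, the Section 7.2 and Appendix 1 visits, and survival follow-up to cover the later boosters.

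**Cost.** Amendment wording if one year is chosen; added scans, visits and survival follow-up for at most 10 patients if two years is chosen. Cohort 5 may start about 3 weeks later (19 to 35 days) where Section 8.1's floor would have applied anyway, or about 6 weeks later (40 to 56 days) against the Section 6 sentence alone. A one-year limit removes up to 8 − 4 = 4 optional boosters from a patient still on treatment.

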- 3) Cohort 3: Six patients will receive Ad5 [E1-, E2b-]-CEA(6D) at a dose of 1×10^{11} particles in 0.5 mL SQ in the same thigh every 3 weeks for 3 immunizations. Immunizations site should be separated by 5 cm. A diary card will be given to each subject at the first treatment along with a ruler to record any adverse reactions for 2 days after treatment (24 hours and 48 hours post injection). The diary card will be placed in the study file. Assessment of DLT for proceeding to phase II enrollment (Cohort 4) will be made after all patients in this cohort have had a study visit at least 3 weeks after receiving their first dose of vaccine. If there is 0 or 1 DLT, then subjects may enroll in Cohort 4. If 2 patients have DLT at this dosage level, the dosage level in cohort 2 will be considered the MTD. If only 3 patients were enrolled in cohort 2, an additional 3 patients will be enrolled at that dosage before proceeding to the next level.
- 4) Phase II cohort (Cohort 4): After the MTD is established, an additional 12 patients will receive Ad5 [E1-, E2b-]-CEA(6D) at the MTD every 3 weeks for 3 immunizations.

Note: if during accrual of patients in the phase II cohort, DLT occurs at a sufficient rate such that the rate of DLT amongst the total number of patients (those treated at MTD in phase I and those in phase II) is $\geq 33\%$, then phase II will be restarted at the dosage level which is one level below the prior MTD.

- 5) Cohort 5: Six patients will receive Ad5 [E1-, E2b-]-CEA(6D) at a dose of 5×10^{11} particles SQ in 2.5 mL every 3 weeks for 3 immunizations. Assessment of DLT will be made after all patients in this cohort have had all 3 injections and been observed for at least 30 days after the last injection. If there are 0-1 DLT, then this will be declared the maximum feasible dose. If there are 2 or more DLT, then 1×10^{11} particles will be declared the MTD.

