6.2. Pharmaceutical Information

6.2.1 Dosage and Administration

Patients will receive Ad5 [E1-, E2b-]-CEA(6D) at a dose of 1×10^9 , 1×10^{10} , or 1×10^{11} virus particles (vp) per immunization in 0.5 mL of sterile saline SQ every 3 weeks for 3 immunizations. The 5th cohort will receive Ad5 [E1-, E2B-]-CEA(6D) at a dose of 5×10^{11} virus particles (vp) per immunization in 2.5 mL of sterile saline SQ every 3 weeks for 3 immunizations. The 6th cohort will receive Ad5 [E1-, E2B-]-CEA(6D) at a dose of 5×10^{11} virus particles (vp) per

immunization in 1.0 mL SQ every 3 weeks for 3 immunizations and each additional boost will be delivered at the same dose.

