7.3.3 Treatment of Toxicity

For acute allergic reactions, use of diphenhydramine 25-50 mg IV, corticosteroids (Solumedrol 100 mg), and epinephrine (1:1000, 0.3-1 mL sq) should be considered. These medications are available in the clinical setting where the vaccine will be administered. For auto-immunity, corticosteroids (prednisone 0.5-1 mg/kg/d) should be considered. Clinical assessment of other targets, such as thyroid, arthritis, urticaria, or proteinuria, for auto-immunity and serum sickness like antigen-antibody complex disease, will also be performed as indicated.

7.3.4 Active Immunotherapy will be Discontinued for:

- 7.3.4.1 Life-threatening anaphylactic reactions related to active immunotherapy
- 7.3.4.2 DLT related to active immunotherapy
- 7.3.4.3 Disease progression (by RECIST criteria). Patients will be offered referral to a medical oncologist for discussion of other treatment options, and for continued medical care.
 - 7.3.4.3.1 Disease progression prior to completing the 3 study immunizations:

In the event that a patient undergoes reimaging studies prior to the completion of their 3 study immunizations and is found to have disease progression, they will be permitted to continue on the study as long as the progression has been 50% or less by RECIST criteria.

If a patient is removed from the study prior to completion of the assigned vaccine schedule for any reason other than toxicity, that patient will be replaced, in order to obtain data to help determine the toxicity of the immunizations. We will allow up to 3 replacements per cohort (Phase I, Dose levels 1 and 2; Phase II, MTD).

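### The running DLT rule in Section 6 omits cohort 6, and the Table 3 counts it points to are wrong on either reading

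*Combined protocol and SAP*

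**What the plan says.** All references are to the current protocol version, the one that adds cohort 6.

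- **Section 6, opening text.** A general sentence lowers the MTD one level when at least 33% of a given cohort have DLT. A second sentence makes the check continuous, but for two cohorts only: "In phase II (Cohort 4) and Cohort 5, if at any time the rate of DLT in patients enrolled is" at or above 33%, the MTD is redefined downwards. Readers are sent to Figures 3A and 3B and Table 3 for details.
- **Section 6, items 1 and 2.** One DLT in the first 3 patients leads to 3 more patients; two DLT lead to de-escalation.
- **Section 6, item 3 (cohort 3, n=6).** "If 2 patients have DLT at this dosage level, the dosage level in cohort 2 will be considered the MTD".
- **Section 6, item 4 (cohort 4, n=12).** The note takes the DLT rate over everyone treated at the MTD, phase I and phase II together.
- **Section 6, item 5 (cohort 5, n=6).** 0-1 DLT is acceptable. "If there are 2 or more DLT", 1x10^11 becomes the MTD.
- **Section 6, item 6.** "Cohort 6: Up to ten (10) patients will receive" 5x10^11 particles in 1.0 mL, with boosters. It gives no DLT assessment time, limit or action. Section 6.2.1 ("The 6th cohort will receive") confirms the dose.
- **Table 3.** The columns are cohorts 1 to 6 with n = 3, 3, 6, 12, 6, 10. The numbers with DLT said to reach 33% are 1, 2, 4, 8, 10, 13.
- **Section 8.1.** "A dosage level will be considered safe if <33% patients treated at a dose level experience DLT": 0 of 3, at most 1 of 6, 3 of 12 or 5 of 18. It adds: "Safety will continue to be monitored among additional patients treated at the MTD in phase II". Cohorts 5 and 6 are not named there.

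**The concern.** Safety is the primary objective, and cohort 6 is the larger of the two groups at the highest dose: up to 10 patients, against 6 in cohort 5. Cohort 5 has a stated limit and is named in the continuous rule; cohort 6 has neither. Anyone who turns to Table 3 for a count during accrual finds 13 under a column headed n=10.

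The rule that stops an individual's vaccination, Section 7.3.4.2 ("DLT related to active immunotherapy"), protects the patient who had the event. It does not tell the team whether the next patient may start.

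**Working it through.** **Inputs.** Column n and printed counts from Table 3; the 33% criterion from Sections 6 and 8.1; DLT limits from Section 6, items 1 to 5.

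**Step 1. Reproduce Table 3.** The count required is the smallest integer x with x/n >= 0.33.

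| Cohort | n | Printed | Printed/n | Needed for n | Cumulative n | Printed/cumulative n | Needed for cumulative n |
|---|---|---|---|---|---|---|---|
| 1 | 3 | 1 | 33.3% | 1 | 3 | 33.3% | 1 |
| 2 | 3 | 2 | 66.7% | 1 | 6 | 33.3% | 2 |
| 3 | 6 | 4 | 66.7% | 2 | 12 | 33.3% | 4 |
| 4 | 12 | 8 | 66.7% | 4 | 24 | 33.3% | 8 |
| 5 | 6 | 10 | 167% | 2 | 30 | 33.3% | 10 |
| 6 | 10 | 13 | 130% | 4 | 40 | 32.5% | 14 |

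*By the printed n*, cohorts 5 and 6 are impossible. Cohorts 3 and 4 stand at twice the 33% count, and cohorts 3 to 5 contradict items 3 and 5 (2 of 6) and Section 8.1 (at most 1 of 6, at most 3 of 12).

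*By cumulative enrolment*, dividing by 3 and rounding to the nearest integer gives 1, 2, 4, 8, 10, 13, which matches all six entries. This is evidently how the row was built. It then pools doses from 1x10^9 to 5x10^11, a ratio of 500, against the per-dose-level criterion in Section 8.1. The last entry also misses the threshold in its own label: 13/40 = 32.5%, and 14/40 = 35% is the first to pass.

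**Step 2. A running count by number evaluable at a dose level.** The same formula gives 1 at 1-3 evaluable, 2 at 4-6, 3 at 7-9, 4 at 10-12, 5 at 13-15 and 6 at 16-18. Table 3 of the preceding protocol version prints exactly this.

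**Step 3. What that count would cost in cohort 6.** Pool cohorts 5 and 6 (same dose, 6 + 10 = 16 patients). Start from 0 or 1 DLT of 6 in cohort 5, with weights proportional to (1-p)^6 and 6p(1-p)^5. Add cohort 6 patients one at a time and pause when the pooled count reaches 3 at 7-9, 4 at 10-12, 5 at 13-15 or 6 at 16.

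- p = 0.10: 0.9^6 = 0.531 and 6(0.1)(0.9^5) = 0.354, so the weights are 0.60 and 0.40. Chance of a pause: 0.017.
- p = 0.20: 0.262 and 0.393, so the weights are 0.40 and 0.60. Chance of a pause: 0.115.

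**Step 4. How often cohort 5 would pass at high rates.** P(0-1 of 6) is 0.36 at p = 0.33 and 0.11 at p = 0.50.

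**The case against.** **Cohort 6 is not unprotected.** A reader might infer from the omission that it has no DLT control. The documents do not support that. The general per-cohort 33% sentence applies to it, so 4 of 10 would fail once assessed. Section 8.1 requires under 33% per dose level and evaluates safety continuously within a cohort. The Grade 4 and death rules and discretionary suspension also reach it. It repeats cohort 5's particle dose, which has its own limit. This stands and narrows the point to the missing running count.

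**The row is a labelling slip, not an instruction to wait for 13 of 10.** Its cumulative origin makes that fair. The slip still leaves a decision table that is wrong by its printed n and, read cumulatively, conflicts with Section 8.1.

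**Cohort 2's entry is defensible.** One might say that it too is twice too high, since 1 of 3 is already 33%. But item 2 expands on 1 DLT and acts on 2, so the printed 2 equals the action count. No error is claimed for that cell. For the same reason, restoring 1 DLT at 1-3 evaluable as a bare trigger would clash with items 1 and 2 and with the 0-1 of 6 allowance in items 3 and 5.

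**Figures 3A and 3B are not shown.** They may contain a cohort 6 count, so its absence is established only for the visible text. They could not make Table 3 correct.

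**Conclusion.** The point holds and should be corrected. The continuous DLT sentence leaves out cohort 6, item 6 sets no limit, and Table 3 is wrong for cohorts 3 to 6 by its column n. Read cumulatively, it is incompatible with Section 8.1 and its last entry is short by one.

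It would be tempting to express the harm as patients spared. With the pooled count, and given a cohort 5 pass, expected cohort 6 starts fall from 10 to 7.9 at a 33% DLT rate and to 5.6 at 50%. But a cohort 5 pass has probability only 0.36 and 0.11 at those rates, so the average saving is about 0.36 x 2.1 = 0.7 and 0.11 x 4.4 = 0.5 patients. Even these figures need each DLT to be known before the next patient starts; the saving is zero if all start first. The case for change rests on the wrong table and the missing count, not on patients saved.

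The pause probabilities assume the same true DLT rate in cohorts 5 and 6, DLT known before the next start, and cohort 6 opening only after 0-1 of 6 in cohort 5. Item 6 does not state that last condition. The DLT rates themselves are assumed values.

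**What to change.** 1. In Section 6, add cohort 6 to the at-any-time sentence, with the rate taken over all patients at 5x10^11 particles (cohorts 5 and 6 combined). This matches Section 8.1 and the pooling by dose in item 4.
2. In Section 8.1, name cohorts 5 and 6 in the sentence on continued monitoring.
3. Replace the Table 3 row with a running count by number evaluable at a dose level: 2 at 4-6, 3 at 7-9, 4 at 10-12, 5 at 13-15, 6 at 16-18. State beside it that 1 DLT among the first 3 leads to expansion to 6, as in items 1 and 2, and that 2 of 6 is the limit for cohorts 3 and 5.

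The cost is two sentences and one table row, with no extra patients or visits. The downside is an occasional earlier pause in cohort 6: about 0.02 at a true DLT rate of 10% and 0.12 at 20%, given 0-1 of 6 in cohort 5. One limit of pooling: 5 of 10 in cohort 6 after none in cohort 5 is 5/16 = 31.3%, which can leave the running count untripped. The general per-cohort rule, which 4 of 10 already fails, should therefore stay in force.
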